# 2.2. Background

In December 2019, a life-threatening infectious disease first observed in Wuhan, China, and later identified as COVID-19 has rapidly spread, causing a global pandemic. According to the World Health Organization (WHO), as of 20 April 2020, 2,314,621 confirmed cases have been reported worldwide with 157,847 deaths (WHO COVID-19 Situation Report 91).

COVID-19 belongs to the coronavirus family of single-stranded RNA viruses that can cross species barriers and can cause illness ranging from the common cold to more severe diseases such as SARS and MERS. Transmission of COVID-19 is believed to occur through respiratory droplets from coughing and sneezing. The pathogenesis is unclear, but the virus seems capable of producing an excessive immune reaction, which results in extensive tissue damage (Rothan and Byrareddy 2020).

The majority of individuals infected with COVID-19 experience a mild respiratory disease generally affecting the lower airways; symptoms usually appear after an incubation period of approximately 5 days. The most common symptoms at onset include fever, fatigue, and dry cough. Other signs and symptoms include myalgia, headache, diarrhea, nausea, dyspnea, lymphopenia, prolonged thrombin time, elevated lactate dehydrogenase, elevated alanine transaminase, and creatine kinase, and bilateral infiltrates on chest imaging. Patients can deteriorate rapidly. The median time from first symptoms to hospitalization is 7 days (Wang D et al. 2020).

Huang et al. (2020) reported that 27% of hospitalized patients diagnosed with COVID-19 infection in China developed ARDS after 9 days from onset of symptoms requiring oxygen therapy and intensive care. Some patients have laboratory evidence of a severe inflammatory response, similar to the cytokine release syndrome, with persistent fever, elevated inflammatory markers (hs-CRP, D-dimer, ferritin), and multiple organ dysfunction (Guan et al. 2020; Chen T et al. 2020). The major complications during hospitalization include ARDS, arrhythmia, and shock. Disease severity and mortality appears to be associated with those over the age of 70 and individuals with underlying comorbidities such as diabetes, hypertension, cardiovascular disease, chronic renal disease, and chronic lung disease (Chen N et al. 2020; Guan et al. 2020; Rothan and Byrareddy 2020; Wang W et al. 2020).

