## 5.3. Method of Assignment to Treatment

Blinding will be maintained in the Phase 3 study.

Method of treatment assignment

Patients who meet all criteria for enrollment will be randomized in a 1:1 ratio (baricitinib 4-mg: placebo) at Day 1.

Randomization will be stratified by these factors:

- disease severity by ordinal scale (OS):
  - hospitalized not requiring supplemental oxygen, requiring ongoing medical care (OS 4)
  - hospitalized requiring supplemental oxygen by prongs or mask (OS 5)
  - hospitalized requiring non-invasive ventilation or high-flow oxygen (OS 6)
- age (<65 years; ≥65 years)
- region (US, Europe, rest of world), and
- dexamethasone and/or other systemic corticosteroid used at baseline for primary study condition (Yes/No). (Note that the original protocol included symptom onset <7 days or ≥7 days prior to randomization as a stratification factor. It was changed to this one in Amendment (c).)

Assignment to treatment groups will be determined by a computer-generated random sequence using an interactive web-response system (IWRS).

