### 6.1.4. Baseline Stratification Variables

Throughout the SAP, when baseline stratification variables are referred to, they include the following categorical variables:

- baseline disease severity (ordinal scale [OS] 4, OS 5, OS 6),
- age (<65 years, ≥65 years),
- region (US, Europe, rest of world) and
- dexamethasone and/or other systemic corticosteroid used at baseline for primary study condition (Yes/No).

If any of these are redundant for a particular model they will be dropped.

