### **6.2.1. Logistic Regression Model**

Treatment comparisons of discrete/binary efficacy variables between treatment groups will be made using a logistic regression analysis adjusted for baseline stratification variables (Section 6.1.4). The p-value and odds ratio with 100(1- $\alpha$ )% confidence interval (CI) from the logistic model will be reported.

Point estimates for proportions and difference in proportions will be presented. Confidence intervals and p-values for the estimates of the differences of the proportions and will be presented. For last-observation-carried-forward (LOCF) analyses the CIs will be based on the Newcombe-Wilson method without continuity correction. For multiple imputation analyses, percentages will be based on the observed percentages; CIs will be based on the Wald method without continuity correction.

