### **6.2.3. Time-to-Event Analysis**

The primary analysis for time-to-event analysis will be the unstratified log-rank test. Treatment comparisons for time-to-event analysis may also be analyzed using a Cox proportional hazards model adjusted for baseline stratification variables (Section 6.1.4). The hazard ratio with 95% CIs will be reported. Kaplan-Meier curves may also be produced. Diagnostic tests for checking the validity of the proportional hazards assumption may be performed. If the assumption of proportional hazards is not justified, a statistical model capable of handling nonproportional hazards will be explored to assess treatment effect, such as a max-combo test (Lee 1996), restricted mean survival time model (Royston and Parmar 2013), and win ratio analysis (Pocock et al. 2012).

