## **6.3. Adjustments for Covariates**

Unless otherwise specified, the statistical analysis models will control for baseline stratification variables (see Section 6.1.4).

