## 6.8. Patient Characteristics

### 6.8.1. Demographics

Patient demographics will be summarized as described above. The following demographic information will be included:

- age
- age group (<65 vs. ≥65)
- age group (<65, ≥65 to <75, ≥75 to <85, ≥85)
- gender (male, female)
- race (American Indian or Alaska Native, Asian, Black or African American, Native Hawaiian or Other Pacific Islander, White, Multiple)
- geographic region (US, Europe, Rest of World)
- country

- weight (kg)
- weight category (<60 kg, ≥60 to <100 kg, ≥100 kg)
- height (cm)
- body mass index (BMI) (kg/m^2)
- body mass index category (<25 kg/m^2, ≥25 to <30 kg/m^2, ≥30 kg/m^2), and
- baseline renal function status: impaired (estimated glomerular filtration rate [eGFR] <60 mL/min/1.73 m^2) or not impaired (eGFR ≥60 mL/min/1.73 m^2).

A listing of patient demographics will also be provided for the ITT population.

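### Covariate-adjusted efficacy models use age only as under 65 versus 65 and over; adding age in years is an optional change with a small gain in power

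*SAP*

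**What the plan says.** SAP 6.1.4 defines the baseline stratification variables as categorical and gives age as "age (<65 years, ≥65 years". This is the cut used in randomization (SAP 5.3: "age (<65 years; ≥65 years").

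The list then governs the adjusted models. SAP 6.3: "Unless otherwise specified, the statistical analysis models will control for baseline stratification variables". SAP 6.2.1, which covers the primary endpoint: "Treatment comparisons of discrete/binary efficacy variables between treatment groups will be made using a logistic regression analysis adjusted for baseline stratification variables". The ANOVA (6.2.2), Cox (6.2.3), proportional-odds (6.2.4) and MMRM (6.2.6) models use the same set, as do the subgroup models in 6.14. The Addendum 5 analyses in Appendix 3 name the same two age groups. No planned efficacy model uses age in years.

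Exact age is available. SAP 6.8.1 lists age itself and a finer grouping, "age group (<65, ≥65 to <75, ≥75 to <85, ≥85", for demographic summaries, and the eGFR formula in Protocol 10.2.2 needs it. On prognosis, Protocol 2.2 says: "Disease severity and mortality appears to be associated with those over the age of 70".

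Some analyses contain no age term at all. SAP 6.2.3: "The primary analysis for time-to-event analysis will be the unstratified log-rank test". Table KHAA.6.5 makes that test the key secondary analysis of time to recovery and of all-cause mortality. The Wilcoxon tests (6.2.5) and the imputation strata (6.4.3) do not use age. For risk differences under multiple imputation, SAP 6.2.1 says: "CIs will be based on the Wald method without continuity correction", with no covariates mentioned.

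**The concern.** With one cut, a patient of 20 counts the same as one of 64, and a patient of 66 the same as one of 90. The age that the protocol singles out, 70, lies inside the upper group, so the models cannot separate patients on either side of it. Stratified randomization balances the two groups but not ages within them.

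What is at stake is efficiency. If age predicts progression within the two groups, the adjusted models leave some explainable variation unused. Sections 5.2 of the SAP and 9.2 of the protocol give only 54% power in the less favourable scenario, so a cheap gain is worth a look.

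**Working it through.** **Step 1: reproduce a stated figure.** Protocol 9.2 gives, for Amendment D, 1000 patients, 25% events on placebo and two-sided alpha 0.05, with power of 83% for a 7.5-point difference and 47% for 5 points. With 500 per arm and pooled variance under the null, power = Φ[(Δ − 1.96·SE0)/SE1].
- 25% vs 17.5%: SE0 = √(2 × 0.2125 × 0.7875/500) = 0.02587; SE1 = √((0.1875 + 0.144375)/500) = 0.02576; Φ[(0.075 − 0.05071)/0.02576] = 82.7%.
- 25% vs 20%: SE0 = 0.02641; SE1 = 0.02636; Φ[(0.05 − 0.05176)/0.02636] = 47.3%.

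Both match, so the 25% rate is a usable base. Amendment E states no placebo rate for its 1400-patient table. The absolute powers below are therefore not comparable with its 81% and 54%; only differences between models matter.

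**Step 2: inputs for the age comparison.** From the documents: 1400 patients, 1:1, stratified at 65; placebo 25%; effects of 7.5 points (17.5% on baricitinib) and 5.4 points (19.6%), the latter being the plan's combined effect, 0.6 × 0.040 + 0.4 × 0.075 = 0.054. Assumed, because the documents give no figure: age about normal with mean 58 and SD 14, and an odds ratio per 10 years of age between 1.0 and 2.0, linear on the logit. There were 1500 simulated trials per scenario. Each was fitted by logistic regression with the two-level age term, then with linear age added. The other stratification factors were left out.

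**Step 3: results.** Relative efficiency = (z with age added / z with two-level age)², where z is the mean estimate over the mean SE. Extra patients = 1400 × (relative efficiency − 1).

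| OR per 10 years | Relative efficiency | Equivalent extra patients | Power, 7.5-point effect | Power, 5.4-point effect |
|---|---|---|---|---|
| 1.0 | 1.00 | 0 | 93.1 → 93.0% | 67.3 → 67.7% |
| 1.2 | about 1.005 | about 7 | 92.3 → 92.7% | 67.1 → 67.1% |
| 1.4 | 1.011–1.013 | 15–18 | 94.0 → 94.5% | 70.2 → 70.1% |
| 1.6 | 1.023–1.025 | 32–35 | 93.1 → 93.3% | 69.1 → 70.3% |
| 2.0 | 1.043–1.05 | 60–70 | 95.3 → 95.8% | 73.5 → 76.0% |

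Differences of a few tenths of a point are simulation noise. As a check on the largest gain, the mean z moves from 2.583 to 2.646, and Φ(2.583 − 1.96) = 73.3% against Φ(2.646 − 1.96) = 75.4%. That is about 2 points, close to the simulated 2.5.

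Other assumed age distributions (mean 55, SD 12; mean 62, SD 16) gave relative efficiencies of 1.01 to 1.05. A second simulation, with baseline severity, steroid use and region also in the model (2500 trials, treatment odds ratio 0.72), gave gains of 0 to 0.7 points at odds ratios of 1.3 to 1.5 per decade and 1.6 points at 1.8 (71.2% to 72.8%).

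**Step 4: where the gain comes from.** At the 7.5-point effect:
- OR 1.4 per decade: SE 0.1342 → 0.1352 (up 0.7%); log odds ratio −0.4652 → −0.4713 (up 1.3% in size). Relative efficiency = [(0.4713/0.1352)/(0.4652/0.1342)]² = 1.011.
- OR 2.0 per decade: SE 0.1390 → 0.1424 (up 2.4%); log odds ratio −0.4949 → −0.5181 (up 4.7% in size).

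The standard error does not fall. The estimate, now conditional on one more covariate, moves away from zero by more than the standard error grows. In the ANOVA analyses of ventilator-free days and hospital stay, a prognostic covariate does lower the residual variance; that gain was not quantified.

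**The case against.** The plan is sound as written. Its models adjust for the factors used in randomization, as Protocol 9.4.1 and 9.4.2 specify, and the SAP follows them. Randomization already protects against bias, so age imbalance within a stratum is chance. The benefit is close to nil for moderate age effects: −0.1 to +0.5 power points at the 7.5-point effect, and none at 5.4 points for odds ratios of 1.2 and 1.4. Every age effect here is assumed. Protocol 2.2 is general background on severity and mortality and does not address the primary endpoint in this population. Population 2, which the SAP revision history describes as much smaller than expected, has least room for extra parameters.

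Most of this stands. There is no error and no bias, and the gain is small. It does not defeat the suggestion, because the cost is smaller still: when age has no effect, relative efficiency is 1.00. Nor does naming the covariates in the protocol block the change. Protocol 9.4 lets changes that are not principal features be made and justified in the SAP and clinical study report.

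**Conclusion.** In the covariate-adjusted efficacy models the two-level age term leaves prognostic information unused. Adding age in years is worth about 0 to 5% in effective sample size for the primary test, or roughly 0 to 2.5 power points. The top of that range needs an odds ratio near 2.0 per decade and the smaller treatment effect. The figures rest on an assumed age distribution, a 25% placebo rate, and an age effect made truly linear in the simulation, which favours a linear term.

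A reader might infer three stronger things that the documents do not support:
- That age in two groups affects every analysis. The key secondary log-rank tests, the Wilcoxon tests and the imputation strata have no age term.
- That the primary analysis gains precision at no cost. The standard error of the log odds ratio rises slightly, and the Wald and Newcombe-Wilson risk-difference intervals, as described, stay the same.
- That the mortality analysis would benefit most. A logistic stand-in with assumed rates of 12% and 8%, and odds ratios of 1.5 to 2.5 per decade, gave relative efficiencies of 1.01 to 1.07 over the two-level term. The planned mortality test is an unstratified log-rank test, which this change leaves untouched; only its supportive Cox model would alter.

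**What to change.** Keep the under-65 / 65-and-over factor. Add one sentence, in SAP 6.3 or after the list in 6.1.4 but separate from it, saying that every efficacy model adjusting for the stratification variables also includes age in years as a single linear covariate. State that the log-rank tests, Wilcoxon tests and risk-difference intervals are unchanged, and whether the Addendum 5 models in Appendix 3 follow the same rule. Fix the wording before the study team is unblinded, and give the justification in the SAP and clinical study report. After unblinding, the model could serve only as a labelled sensitivity analysis.

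The cost is one degree of freedom per model, a linearity assumption, and an odds ratio conditional on one more covariate. Randomization, the alpha split and trial conduct are unaffected.

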## **6.2. Statistical Methods**

The following will be applied to the ITT population as described in Section 6.1.1.

### **6.2.1. Logistic Regression Model**

Treatment comparisons of discrete/binary efficacy variables between treatment groups will be made using a logistic regression analysis adjusted for baseline stratification variables (Section 6.1.4). The p-value and odds ratio with 100(1- $\alpha$ )% confidence interval (CI) from the logistic model will be reported.

Point estimates for proportions and difference in proportions will be presented. Confidence intervals and p-values for the estimates of the differences of the proportions and will be presented. For last-observation-carried-forward (LOCF) analyses the CIs will be based on the Newcombe-Wilson method without continuity correction. For multiple imputation analyses, percentages will be based on the observed percentages; CIs will be based on the Wald method without continuity correction.

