## 9.2. Sample Size Determination

In the protocol amendment C, it was assumed that the proportion of patients progressing to death or non-invasive ventilation/high-flow oxygen or invasive mechanical ventilation (including ECMO) by Day 28 was 28% and 18.5% for placebo and baricitinib, respectively. Accordingly, the sample size was increased to 600 to yield approximately 80% power to detect an absolute difference of 9.5% between the baricitinib treatment group and the placebo treatment group using a two-sided alpha of 0.05 with the provision that sample size may be updated in a blinded manner during the study from 600 up to approximately 1000, if warranted based on newly available external study data. This would include the various differing factors amongst the studies, including, for example, the ACTT-2 results.

In protocol amendment D, the sample size is updated based on newly available data from the ACTT-2 study (ACTT-2 press release 2020). Based on the emerging data and evolving therapeutic options for standard of care, the assumption for the proportion of patients in the placebo group progressing to death or non-invasive ventilation/high-flow oxygen or invasive mechanical ventilation (including ECMO) by Day 28 is revised to approximately 25%. The sample size of 1000 patients will yield approximately 47% power to detect an absolute difference of 5% and 83% power to detect an absolute difference of 7.5% between the baricitinib treatment group and the placebo treatment group using a two-sided alpha of 0.05.

In protocol amendment E, the sample size is updated to approximately 1400 patients based on blinded review of the proportion of patients requiring oxygen supplementation without the use of dexamethasone or systemic corticosteroids at baseline and the potential that concomitant use of systemic corticosteroids may reduce the magnitude of the treatment effect.

The table below describes the power calculations for various scenarios with a total sample size of 1400. This assumes, for illustration, that  $\alpha_1$  for Population 1 is 75% of the total alpha and that 60% of the patients were taking dexamethasone or other corticosteroids at baseline.

-	atients who are at OS 5 or baseline	Combined Effect Size	Power for at least one of the two primaries to succeed
Patients using dexamethasone or a systemic corticosteroid	Patients not using dexamethasone or a systemic corticosteroid		
0.075	0.075	0.075	81%
0.040	0.075	0.054	54%

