## 5.2. Determination of Sample Size

In protocol amendment e, the final amendment, the sample size was updated to approximately 1400 patients based on blinded review of the proportion of patients requiring oxygen supplementation without the use of dexamethasone or systemic corticosteroids at baseline and the potential that concomitant use of systemic corticosteroids may reduce the magnitude of the treatment effect.

The table below describes the power calculations for various scenarios with a total sample size of 1400. This assumes, for illustration, that  $\alpha_1$  for Population 1 is 75% of the total alpha and that 60% of the patients were taking dexamethasone or other corticosteroids at baseline.

Treatment Effect Size in Patients Who are at OS 5 or OS 6 at Baseline		Combined Effect Size	Power for at Least One of the Two Primaries to Succeed
Patients using dexamethasone or a systemic corticosteroid	Patients not using dexamethasone or a systemic corticosteroid		
0.075	0.075	0.075	81%
0.040	0.075	0.054	54%

Abbreviations: NIAID = National Institute of allergy and Infectious Diseases; OS 5 = #5 on the 8-point NIAID ordinal scale - Hospitalized, requiring supplemental oxygen; OS 6 = #6 on the 8-point NIAID ordinal scale – Hospitalized, on noninvasive ventilation or high-flow oxygen devices.

Note: Power estimates were obtained from a custom simulation program.

Amendment e also allowed for the sample size to be increased using an unblinded sample size re-estimation (Gao et al. 2008) during an interim analysis (that occurred in January 2021).

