## 6. A Priori Statistical Methods

### 6.1. General Considerations

Unless otherwise specified, efficacy analyses will be conducted on the Intent-to-Treat (ITT) Population. Patients will be analyzed according to the treatment to which they were assigned. All tests of treatment effects will be conducted at a 2-sided alpha level of 0.05, unless otherwise stated.

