### 6.11.1. Primary Outcome and Methodology

The primary comparison of interest is the proportion of patients who die or require non-invasive ventilation/high-flow oxygen or invasive mechanical ventilation (including ECMO) by Day 28. The primary comparison will be performed on two different populations:

- Population 1 – all randomized patients
- Population 2 – patients who, at baseline, require oxygen supplementation and are not receiving dexamethasone or other systemic corticosteroids for the primary study condition.

Patients on non-invasive ventilation/high-flow oxygen at baseline will be counted toward this endpoint if they progressed to invasive mechanical ventilation. Treatment comparisons between baricitinib 4-mg QD + background therapy and placebo + background therapy will be made using logistic regression with baseline stratification factors and treatment group in the model.

- Pr.V: Proportion of patients who died or require non-invasive ventilation/high-flow oxygen or invasive mechanical ventilation (including ECMO) by Day 28. For patients who start with ventilation at baseline, the patients need to be worsening in symptom (at least 1-point worsening in NIAID-OS) to be counted.

For the primary comparison involving two different populations, the alpha will be split between the two populations such that 99% of alpha is assigned to Population 1 and the rest to Population 2. The primary endpoint will be met if any one or both of these two populations show a significant treatment effect.

If the sample size is increased as a result of the interim analysis, the Cui, Hung, and Wang (CHW) procedure (Cui et al. 1999) will be applied to the primary endpoints for the two populations and the secondary endpoints to control the type I error at a one-sided  $\alpha=0.025$  significance level. The CHW method ensures strong control of type I error when the sample size is increased in a data dependent manner. Details about the CHW statistics are provided in Section 6.16.2.4.

If the sample size is increased as a result of the interim analysis, an unadjusted point estimate for both of the primary efficacy analysis will be calculated and reported. A median unbiased point estimate and a stage-wise adjusted confidence interval for the primary efficacy analysis will be calculated and reported based on the approach described by Brannath and colleagues (Brannath et al. 2009) to assess sensitivity of the point estimate.

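### The difference in proportions gets an unadjusted confidence interval and a p-value with no stated method, although randomization is stratified and the primary test is adjusted for the same factors

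*SAP*

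**What the plan says.** Patients are "randomized in a 1:1 ratio (baricitinib 4-mg: placebo) at Day 1". Allocation is stratified by baseline ordinal-scale severity (OS 4, 5, 6), age, region and baseline steroid use (SAP 5.3). SAP 6.11.1 bases the primary comparison on logistic regression with those factors in the model. SAP 6.3 makes adjustment the default: "the statistical analysis models will control for baseline stratification variables".

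SAP 6.2.1 then adds a second presentation of each binary endpoint, the difference in proportions: "Confidence intervals and p-values for the estimates of the differences of the proportions and will be presented". For LOCF analyses the interval is Newcombe-Wilson. For multiple-imputation analyses the percentages are the observed ones and "CIs will be based on the Wald method without continuity correction". These methods are given for intervals only; none is given for the p-value of the difference. Neither the rest of the SAP nor protocol 9.4.1 names a stratified, Mantel-Haenszel or model-standardised difference.

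By SAP Table KHAA.6.5, this covers the primary endpoint and one-point improvement (both multiple imputation) and the oxygen-saturation response (LOCF).

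On the threshold, SAP 6.1 says: "All tests of treatment effects will be conducted at a 2-sided alpha level of 0.05, unless otherwise stated". For the primary comparison, "99% of alpha is assigned to Population 1 and the rest to Population 2".

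**The concern.** A Wald or Newcombe-Wilson interval on raw percentages treats the arms as two simple random samples. Allocation stratified by prognostic factors removes the between-stratum part of the variance of the difference. The unadjusted standard error keeps that part and so overstates the uncertainty.

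Two things are at stake. Protocol 9.2 sizes the trial on absolute differences, so readers will look to this interval for the size of the effect, and it may be wider than the design warrants. Also, one endpoint will carry an adjusted test, an unadjusted interval and an undefined second p-value. Near the threshold these can point in different directions with no stated order of precedence.

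**Working it through.** **Inputs from the documents.** Total sample size: "the sample size was updated to approximately 1400 patients based on blinded review", taken as 700 per arm. The protocol 9.2 assumption for placebo patients with an event "by Day 28 is revised to approximately 25" percent. Steroid use 60%, the illustration in SAP 5.2. Number of strata: 3 × 2 × 3 × 2 = 36.

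**The plan's own figures.** Amendment D has 500 per arm, two-sided 0.05 and 25% placebo events. Power = Φ{[δ − 1.96·√(2p̄(1−p̄)/n)] / √[p0(1−p0)/n + p1(1−p1)/n]}.
- δ = 0.05: (0.05 − 1.96 × 0.02641)/0.02636 = −0.067, so power is 47.3% (stated 47%).
- δ = 0.075: (0.075 − 1.96 × 0.02587)/0.02576 = 0.943, so power is 82.7% (stated 83%).

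The sizing is thus on the absolute scale. The Amendment E powers come from a custom simulation with no stated placebo rate and are not used here.

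**Unadjusted interval at 1400 patients, 25% against 17.5%.** Half-width = 1.96·√(0.25·0.75/700 + 0.175·0.825/700) = 1.96 × 0.02177 = 0.0427, or 4.3 points.

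**Why it is conservative.** p(1−p) is the average within-stratum variance plus the between-stratum variance of risk, and stratified allocation removes the second part. Take assumed placebo risks of 7.6/20.9/45.4% in OS 4/5/6 with shares 15/60/25%. The between-stratum variance is 0.15·0.174² + 0.60·0.041² + 0.25·0.204² = 0.0160, which is 8.5% of 0.1875. Severity alone then inflates the standard error by 1/√(1 − 0.085) = 1.045. The other factors add to that.

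**Simulation.** 4000 trials per setting; permuted blocks of 4 within the 36 cells; true differences of 0, 3, 5 and 7.5 points. Assumed, because the documents do not give them: OS shares as above, 33% aged 65 or over, regions 22/18/60%, no missing data, and prognostic strength from none to strong. The comparator is the standardised difference d = (1/N)Σ[p̂(1,xᵢ) − p̂(0,xᵢ)] from the adjusted logistic model, with standard error √(Σ IFᵢ²)/N, where IFᵢ is the influence function.

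| Prognostic strength | Placebo risk, OS 4/5/6 | Unadjusted SE ÷ standardised SE | Half-width at 7.5 points: standardised (unadjusted 4.3) | Coverage of unadjusted 95% CI | Adjusted test significant, unadjusted CI includes 0 (3 to 7.5 points) | Same, as share of significant adjusted tests |
|---|---|---|---|---|---|---|
| None | 25/25/25% | 1.002 | 4.25 | about 95% | 0.1-0.2% | 0.1-0.9% |
| Weak | 19/24/30% | 1.008 | 4.23 | about 95% | 0.2-0.5% | 0.2-1.6% |
| Moderate | 13/23/37% | 1.026-1.029 | 4.16 | 95-95.5% | 0.8-2.1% | 0.8-6.5% |
| Strong | 8/21/45% | 1.062-1.069 | 4.01 | 96-96.6% | 1.5-4.8% | 1.5-14% |

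The Monte Carlo error of a coverage figure is √(0.95·0.05/4000) = 0.3 points. The reverse conflict, where the unadjusted interval excludes zero but the adjusted test is not significant, occurs in 0.3% of trials or fewer.

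Two further results help interpretation.
- The point estimate hardly changes in precision. In the strong, no-effect setting the empirical SD is 0.02184 unadjusted and 0.02181 standardised. The unadjusted SE is 0.02313 and the standardised SE 0.02164. The gain is an SE that matches the design.
- With no true effect, the adjusted test rejects in the favourable direction in 2.35-2.57% of trials, in line with 2.5%.

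**The case against.** The strongest reply is that nothing decisive rests on this interval. Success is defined on the adjusted logistic test, and the difference in proportions accompanies it. Protocol 9.4.1 planned exactly that pairing. A conditional odds ratio and a marginal difference need not agree at a threshold, and a slightly wide interval guards against overclaiming. All of this stands, and it limits the point to estimation and reporting.

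The reply also bears on three stronger readings that a reader might reach.

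- *The second p-value is crude.* SAP 6.2.1 does not say so. It names methods for intervals only, and the default in SAP 6.3 leaves an adjusted p-value possible. What can be said is that the method is missing.
- *The interval is too wide by a fixed amount, such as 7%.* That figure belongs to strongly prognostic strata, and the documents give no stratum event rates. The endpoint rule could flatten the gradient: OS 4 and 5 patients count on reaching OS 6, whereas OS 6 patients must reach OS 7 or die. If the factors are weak, the excess is below 1%.
- *A conflict between interval and test undermines the trial's conclusion.* It cannot, because SAP 6.11.1 settles success on the logistic test.

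The simulated conflicts use two-sided 0.05. Population 1's initial level before the correlation adjustment is 0.99 × 0.025 = 0.02475 one-sided, or 0.0495 two-sided, so this simplification matters little.

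What the reply does not remove is that the analysis already uses these factors for the test and ignores them for the interval, with no reason given.

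**Conclusion.** The point holds as a free improvement. The interval for the difference in proportions is unadjusted, while the design and the test both use the stratification factors, and a second p-value is promised without a method. The interval is valid and conservative. It is about 0-7% wider than a standardised one, at most about 0.3 points on a half-width of 4.3 (4.3 − 4.01), with coverage of about 95-96.6%. Disagreement with a significant adjusted test occurs in about 0.1-5% of trials for true differences of 3 to 7.5 points.

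These sizes rest on the assumed severity, age and region mix, the assumed prognostic strengths, a 25% placebo rate and complete data, for Population 1 at 1400 patients. The direction needs only that the factors are prognostic. The documents do not support any claim that type I error, the success rule or the validity of the interval is compromised.

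**What to change.** In SAP 6.2.1, for the primary and binary key secondary endpoints:

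1. Report the standardised (marginal) risk difference from the same adjusted logistic model: average each patient's predicted risk under both arms and take the difference. A Mantel-Haenszel difference over the strata is an acceptable alternative.
2. Give it a matching robust or influence-function standard error. Under multiple imputation, pool estimate and variance over the 100 datasets by Rubin's rules. Under LOCF, apply the same estimator to the single dataset.
3. Keep crude percentages as description only.
4. Drop the second p-value, or state its method and label it non-confirmatory.

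Step 2 also settles a neighbouring mismatch: under multiple imputation, SAP 6.2.1 takes percentages from observed data, while SAP 6.14 takes them from the imputed datasets.

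The cost is SAP wording and a short program. No new data are needed, and the primary test stays as it is.
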